6. STUDY DRUG

Patients will be randomized in a 1:1 ratio to receive study treatment with either Arm 1: brentuximab vedotin, or Arm 2: bexarotene or methotrexate (for bexarotene-treated patients, study treatment will include pretherapy with fenofibrate, per Section 6.2.2). All protocol-specific criteria for administration of study drug must be met and documented prior to drug administration. Study drug will be administered only to eligible patients under the supervision of the investigator or identified subinvestigator(s).

6.1 Brentuximab vedotin Administration

Study treatment will be administered by IV infusion given over approximately 30 minutes on Day 1 of each 21-day cycle. In the absence of infusion toxicities, the infusion rate for all patients must be calculated in order to achieve a 30-minute (approximate) infusion period. Brentuximab vedotin must not be administered as an IV push or bolus. Study treatment will be administered through a dedicated IV line and cannot be mixed with other medications.

The dose of brentuximab vedotin is 1.8 mg/kg. Dosing is based on patients' weight according to the institutional standard; however, doses will be adjusted for patients who experience a $\geq 10\%$ change in weight from baseline. Actual weight will be used except for patients weighing greater than 100 kg; dose will be calculated based on 100 kg for these individuals. The dose will be rounded to the nearest whole number of milligrams.

Further brentuximab vedotin administration information can be found in the Pharmacy Manual.

6.2 Reference/Control Therapy

6.2.1 Methotrexate

Methotrexate will be given once weekly as a single dose of 5 to 50 mg orally. Dosages may be gradually adjusted to achieve optimal clinical response but must not exceed 50 mg/week. Once optimal clinical response is achieved, the methotrexate dosage should be decreased to the lowest effective dose. For patients deriving benefit, methotrexate dosing should be continued up to 48 weeks. For further dose modification guidelines, refer to the methotrexate product label.

Further Guidelines for Methotrexate Use

Methotrexate cytotoxicity is highly dependent on the absolute drug concentration and the duration of drug exposure. MTX is actively transported across cell membranes. At serum methotrexate concentrations exceeding 0.1 µmol/mL, passive diffusion becomes a major means of intracellular transport of MTX. The drug is widely distributed throughout the body with the highest concentration in the kidney, liver, spleen, gallbladder, and skin. After oral administration, approximately 60% of a 30-mg/m² dose is rapidly absorbed from the GI tract, with peak blood levels at 1 hour. Even at low doses absorption may be very erratic, varying between 23% and 95%. MTX is excreted primarily by the kidneys via glomerular filtration and active secretion into the proximal tubules. Renal clearance usually equals or exceeds creatinine clearance. Small amounts are excreted in the feces.

Methotrexate Toxicity

When MTX toxicity occurs, the dosage should be modified.

- A 50% dose reduction of MTX is indicated when severe mouth ulcerations occur.

Dose modifications for hyperbilirubinemia are described in [Table 6-1](#).

Table 6-1 Methotrexate Dose Modifications for Hyperbilirubinemia

Severity	Methotrexate Action
Total bilirubin > 1.5 - ≤ 3 mg/dL with an abnormal direct bilirubin	Reduce MTX to 50% of previous dose
Total bilirubin > 3 - ≤ 5 mg/dL	Reduce MTX to 25% of previous dose
Total bilirubin > 5 mg/dL	Discontinue MTX

Brentuximab vedotin (SGN-35)**Clinical Study Protocol C25001 Amendment 5, EudraCT: 2010-024215-14**

Reported MTX-associated toxicities, categorized by frequency and onset time relative to MTX dosing, are presented in [Table 6-2](#).

Table 6-2 Methotrexate-Associated Toxicities

	Common (> 10%)	Occasional (1%-10%)	Rare (< 1%)
Immediate: Within 1-2 days of receiving drug	Transaminase elevations	Nausea, vomiting, anorexia	Anaphylaxis, chills, fever, dizziness, malaise, drowsiness, blurred vision, acral erythema, urticaria, pruritus, toxic epidermal necrolysis, Stevens-Johnson Syndrome, tumor lysis syndrome, seizures, photosensitivity
Prompt: Within 2-3 weeks, prior to the next course		Myelosuppression, stomatitis, gingivitis, photosensitivity, fatigue	Alopecia, folliculitis, acne, renal toxicity (ATN, increased creatinine/BUN, hematuria), enteritis, GI ulceration and bleeding, acute neurotoxicity (headache, drowsiness, aphasia, paresis, blurred vision, transient blindness, dysarthria, hemiparesis, decreased reflexes) diarrhea, conjunctivitis
Delayed: Any time later during therapy, excluding the above conditions		Learning disability	Pneumonitis, pulmonary fibrosis, hepatic fibrosis, osteonecrosis, leukoencephalopathy, pericarditis, pericardial effusions, hyperpigmentation of the nails
Late: Any time after the completion of therapy			Progressive CNS deterioration
Unknown Frequency and Timing	Methotrexate crosses the placenta. Fetal toxicities and teratogenic effects of methotrexate have been noted in humans. The toxicities include: congenital defects, chromosomal abnormalities, severe newborn myelosuppression, low birth weight, abortion, and fetal death. Methotrexate is excreted into breast milk in low concentrations		

6.2.2 Bexarotene

The risks of bexarotene therapy should be considered by the investigator when selecting an appropriate Arm B treatment. The recommended total dose of bexarotene capsules is 300 mg/m²/day. The Mosteller formula or the Dubois and Dubois formula should be used for all body surface area (BSA) determinations for each patient, and are provided in Section 15.2. Dosage should be rounded to the nearest 75 mg. Bexarotene capsules should be taken as a single oral daily dose with a meal. The dose of bexarotene may be reduced to 200 mg/m²/day PO then to 100 mg/m²/day PO, or temporarily suspended, if clinical toxicity occurs. When toxicity is controlled, doses may be restarted and carefully increased. Bexarotene capsules should be continued as long as the patient is deriving benefit, up to 48 weeks. For further dose modification guidelines, refer to the bexarotene product label.

Further Guidelines for Bexarotene Use

Hypertriglyceridemia of all grades has been recorded in 79% of patients who took bexarotene in a study in early-stage CTCL; hypercholesterolemia occurred in 48% of patients; and hypothyroidism in 40%. Similarly, in a study in advanced-stage CTCL, the incidence of hyperlipidemia of all grades (primarily hypertriglyceridemia) with bexarotene was 82%, hypercholesterolemia was 30%, and hypothyroidism was 29%. Before initiating bexarotene therapy, a patient history should be taken to identify those with familial hypertriglyceridemia, uncorrected hypothyroidism, an individual or family history of myocardial infarction or cardiovascular events, or a history of diabetes. A minority of patients with familial hypertriglyceridemia cannot tolerate bexarotene and should be considered for alternative therapy. A substantial proportion of patients will have pathology related to cardiovascular atherosclerosis or a history of cardiovascular disease and have hypertriglyceridemia that will need to be treated before bexarotene therapy. In addition, those with coronary heart disease are likely to have active atherosclerotic plaques that should be stabilized with low-dose statin therapy (eg, 10 mg daily) 3 days before beginning bexarotene. Diabetes can also contribute to the development of coronary heart disease and should be controlled. These groups of at-risk patients are identified by elevated plasma lipid levels and should be monitored particularly closely during treatment, with measurement of fasting lipid levels at weekly intervals for as long as necessary until it becomes apparent that these are stabilized reliably at the levels recommended.

Prior to dosing with bexarotene, attempts should be made to obtain triglyceride levels that meet the normalized lipid levels per the United States Prescribing Information (USPI)

Brentuximab vedotin (SGN-35)**Clinical Study Protocol C25001 Amendment 5, EudraCT: 2010-024215-14**

guidelines. Baseline free T4, TSH and fasting levels of triglycerides, LDL-cholesterol, and HDL-cholesterol should be obtained in all patients being considered for bexarotene treatment and, if elevated, these should be normalized before the therapy is initiated. Ideally, normalization of lipid levels should be achieved through lifestyle changes: adopting a healthy diet low in calories, sugar, saturated fat, and alcohol, and high in fiber and unsaturated fat, along with increased exercise, and weight loss in obese patients. However, achieving compliance with lifestyle changes is difficult and, particularly in a patient with rapidly progressing CTCL, the physician may wish to begin bexarotene therapy as soon as possible. Many patients will therefore require therapy with lipid-lowering agents, such as a fibrate or high-dose omega-3 fatty acids for high triglycerides, a statin to normalize high LDL-cholesterol.⁽⁴³⁾

All patients (with normal or normalized triglyceride levels) who are to be given bexarotene should receive 7 days of pretherapy with fenofibrate 145 to 200 mg daily (the dose should be reduced to 100 mg or even 50 mg daily if creatinine is $> 1.5 \text{ mg dL}^{-1}/0.133 \text{ } \mu\text{mol L}^{-1}$, or in nephrotic syndrome). The fibrate gemfibrozil is not recommended for administration with oral bexarotene, as it results in higher plasma levels of bexarotene and an elevation of triglycerides. Fibrates are contraindicated in patients with liver and kidney failure and in pregnancy, and they potentiate the action of warfarin. They are also associated with a number of reversible adverse effects, including increased liver transaminases and muscular creatine kinase, which may lead to muscle pain. Should these events occur, fibrate treatment should be discontinued.

Most patients do not require a statin at this stage, as the increase in triglycerides with bexarotene therapy is generally more problematic than the increase in LDL-cholesterol level. In addition, patients should be advised on dietary and lifestyle changes that may help to reduce the need for lipid-lowering drugs during treatment.

[figure not shown]
Bexarotene therapy results in a dose-related reduction in thyroid hormone levels through an initial, rapid suppression of TSH gene expression, which leads to central hypothyroidism. This effect is reversible within several days of cessation of therapy. While measurement of TSH levels can provide a useful tool to assess patient compliance, it is essential to monitor free T4 and to keep this hormone within the normal range. At the recommended dose of 300 mg/m^2 daily, most patients experience a decrease in free T4 concentration to $\geq 25\%$ below the normal range, and TSH decreases to the low-normal or even subnormal levels. In anticipation of this, low-dose thyroxine (levothyroxine 0.05 mg daily) should be initiated along with the bexarotene. Correcting hypothyroidism with hormone replacement during

Brentuximab vedotin (SGN-35)

Clinical Study Protocol C25001 Amendment 5, EudraCT: 2010-024215-14

bexarotene therapy will ease hypertriglyceridemia by increasing lipid clearance and can stabilize triglyceride levels. In addition, patients feel less fatigued if thyroxine is supplemented. Based on measurements of free T4, fasting cholesterol, and triglycerides at Days 7, 14, 28, 35, and 49 after initiation of bexarotene therapy, the doses of thyroxine and lipid-lowering therapy should be adjusted as necessary with the target of achieving normal levels of T4 5-12 $\mu\text{g dL}^{-1}$ (64-154 nmol L^{-1}), triglycerides $\leq 200 \text{ mg dL}^{-1}$ (2.2 mmol L^{-1}), LDL-cholesterol $\leq 160 \text{ mg dL}^{-1}$ (4.2 mmol L^{-1}), and HDL-cholesterol $\geq 50 \text{ mg dL}^{-1}$ (1.3 mmol L^{-1}). As patients on bexarotene may metabolize T4 more rapidly, the final daily dose of thyroxine required to keep free T4 within the normal range may be as high as 0.20 to 0.25 mg daily, depending on the patient's age and weight. Monitoring of lipids and free T4 should continue subsequently every 1 to 2 months during treatment. If the bexarotene dose is modified at any time, the doses of thyroxine and antilipid therapy will need to be adjusted accordingly.^(36, 44, 45, 46, 47, 48, 49, 50, 51, 52, 53, 54, 55, 56, 57, 58, 59)

Figure 6-1 Bexarotene Risk Mitigation

Abbreviations: HDL = high-density lipoprotein; LDL = low-density lipoprotein.

Suggested approach to minimize adverse events with bexarotene in patients with cutaneous T-cell lymphoma with normal (or normalized) free thyroxine (T4), fasting triglyceride and cholesterol levels at start of therapy.⁽⁴³⁾

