7.4.18 Pharmacokinetic Measurements

Pharmacokinetic measurements will be made in all brentuximab vedotin-treated patients. Pharmacokinetic parameters to be estimated may include, but are not limited to, the maximum concentration for MMAE (C_{max}) and concentration at the end of infusion for brentuximab vedotin (C_{coi}). Population pharmacokinetics methodologies will be used to

Brentuximab vedotin (SGN-35)**Clinical Study Protocol C25001 Amendment 5, EudraCT: 2010-024215-14**

determine PK parameters and covariates in this population. Efficacy parameters will be related to brentuximab vedotin exposure in the patients.

The incidence of ATA to brentuximab vedotin will also be assessed (See Section 7.4.19).

Table 7-7 presents the sample collection time points. Refer to the Research Specimen Manual for information on collection, processing, storage, and shipment of samples.

Table 7-7 Pharmacokinetic Sampling Time Points

Cycle	Study Day	Time	Window	Relative Time	PK	ATA
Arm 1 (All patients randomized to receive brentuximab vedotin)						
1, 3, 5, 7, 9, 11, 13, 15	1	Predose	Within prior 4 hrs	Start of SGN-35 infusion	X	X
		30 mins Postdose	± 25 mins	End of SGN-35 infusion	X	
EOT Visit	n/a	n/a	n/a	n/a	X	X
Group A^a (half of patients randomized to receive brentuximab vedotin)						
1 and 3	2	24 hr	± 4 hr	Start of SGN-35 infusion	X	
	4	72 hr	± 4 hr	Start of SGN-35 infusion	X	
Group B^a (half of patients randomized to receive brentuximab vedotin)						
1 and 3	3	48 hr	± 4 hr	Start of SGN-35 infusion	X	
	5	96 hr	± 4 hr	Start of SGN-35 infusion	X	

Abbreviations: ATA = antitherapeutic antibodies; EOI = end of infusion; EOT = end of treatment; hr = hour; min = minutes; n/a = not applicable; PK = pharmacokinetic.

a Patients randomized to brentuximab vedotin will be assigned to Group A or B at the time of randomization for PK sampling.

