Added text: Pharmacokinetic measurements will be made in all brentuximab vedotin-treated patients. Pharmacokinetic parameters to be estimated may include, **but are not limited to**, the maximum concentration for MMAE (C_{max}) and concentration at the end of infusion for brentuximab vedotin (C_{ei}).

Purpose: Clarify text regarding the amount of blood to be collected for germline DNA assessments

The primary change occurs in Section 7.4.22, [Germline DNA Polymorphism Assessment](#):

Added text:

Purpose: Clarify text regarding the discontinuation of study drug

The primary change occurs in Section 7.7, [Discontinuation of Treatment With Study Drug, and Patient Replacement](#):

Formerly read: ~~At the time of study drug discontinuation~~, all study procedures outlined for the End of Treatment visit will be completed. The primary reason for study drug discontinuation will be recorded on the eCRF.

Now reads: **Once study drug has been discontinued**, all study procedures outlined for the End of Treatment visit will be completed **as specified in the Schedule of Events**. The primary reason for study drug discontinuation will be recorded on the eCRF.

Purpose: Revise text describing safety analysis

The primary change occurs in Section 8.1.9, [Safety Analysis](#):

Formerly read: Safety will be evaluated by the incidence of ~~TEAEs~~, severity and type of AEs, and by changes from baseline in the patient's vital signs, ECOG performance status, and clinical laboratory results using the safety population. Exposure to study drug and reasons for discontinuation will be tabulated.

~~Treatment-emergent AEs will be tabulated by primary system organ class (SOC), high-level term (HLT), and preferred term. A TEAE is defined as any AE that occurs after administration of the first dose of study drug and up through 30 days after the last dose of study medication. Adverse events will be tabulated according to the Medical Dictionary for Regulatory Activities (MedDRA) by system organ class (SOC), high-level terms, and preferred terms (PTs) and will include the following categories:~~

- TEAEs
- Study drug-related TEAEs
- Grade 3 or higher TEAEs
- Grade 3 or higher study drug-related TEAEs
- ~~TEAEs resulting in study drug discontinuation~~
- ~~SAEs, including study drug-related SAEs~~

~~The most commonly reported TEAEs (ie, those events reported by $\geq 10\%$ of all patients) will be tabulated by high-level term and PT.~~

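### As rendered, the fenofibrate dose-reduction threshold in Protocol 6.2.2 gives an SI creatinine value about 1000 times too small

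*Protocol*

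**What the plan says.** Protocol 6.2.2, under the further guidelines for bexarotene use, gives every bexarotene patient 7 days of fenofibrate at 145 to 200 mg daily. It lowers this to 100 mg or 50 mg daily "if creatinine is $> 1.5 \text{ mg dL}^{-1}/0.133 \text{ } \mu\text{mol L}^{-1}$, or in nephrotic syndrome". Protocol section 6 makes the lead-in part of the assigned treatment: "for bexarotene-treated patients, study treatment will include pretherapy with fenofibrate".

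The SI form of this threshold appears nowhere else in the readable text. SAP 5.7.2 repeats the 145 to 200 mg lead-in without the creatinine rule. The readable part of the Amendment 5 summary of changes (Protocol 15.6) does not mention it, so this is current wording. Figure 6-1, captioned "Suggested approach to minimize adverse events with bexarotene", is not shown and could not be checked.

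**The concern.** A dosing instruction that states one threshold in two unit systems should give the same threshold in both. Here the two figures lie on opposite sides of any realistic creatinine value: the mg/dL figure selects patients with raised creatinine, and the SI figure selects everyone.

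Protocol 4.2 plans about 50 centers globally, and a site whose laboratory reports in SI units would look to the second figure. Followed literally, it would put every bexarotene patient on the reduced fenofibrate dose. The harm would be weaker lipid protection before bexarotene, not excess fibrate in patients with poor renal function.

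**Working it through.** **Inputs**

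- From Protocol 6.2.2: creatinine 1.5 mg/dL, paired with 0.133 µmol/L.
- Assumed, because the documents give no molar masses: creatinine 113.12 g/mol (range tried 113.0 to 113.2), triglyceride 885.4, cholesterol 386.65, T4 776.87.

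**Can the printed SI value be reproduced?**

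Formula: mmol/L = (mg/dL × 10) / molar mass, and µmol/L = mmol/L × 1000.

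- 1.5 mg/dL = 15 mg/L, and 15 / 113.12 = 0.1326 mmol/L = 132.6 µmol/L. Across the molar-mass range the result is 132.5 to 132.7 µmol/L.
- Against the printed value: 132.6 / 0.133 = 997. In µmol/L the figure is not reproduced.
- Read as mmol/L: 0.133 / 0.1326 = 1.003, a difference of +0.3%. In mmol/L it is reproduced to rounding.
- In reverse: 0.133 µmol/L is 0.0015 mg/dL, while 133 µmol/L is 1.50 mg/dL.
- For the printed pair to be equal, the molar mass would have to be 0.015 g/L / (0.133 × 10⁻⁶ mol/L), or about 112,800 g/mol. No choice of constant or rounding explains the gap.

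**Do the other unit pairs in the same section agree?**

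| Quantity | Conventional | Computed SI | Printed SI | Printed vs computed |
|---|---|---|---|---|
| Triglycerides | 200 mg/dL | 2.26 mmol/L | 2.2 | −2.6% |
| LDL-cholesterol | 160 mg/dL | 4.14 mmol/L | 4.2 | +1.5% |
| HDL-cholesterol | 50 mg/dL | 1.29 mmol/L | 1.3 | +0.5% |
| T4, lower limit | 5 µg/dL | 64.4 nmol/L | 64 | −0.6% |
| T4, upper limit | 12 µg/dL | 154.5 nmol/L | 154 | −0.3% |

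All five agree within 3%. The creatinine pair is an isolated slip.

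**Can the threshold apply to an enrolled patient?**

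Inclusion criterion 8 (Protocol 5.1) requires creatinine clearance above 40 mL/min and sets no cap on serum creatinine. As an illustration, take the Cockcroft-Gault formula (an assumption; the protocol names none) for a 60-year-old man of 80 kg with creatinine 1.6 mg/dL: (140 − 60) × 80 / (72 × 1.6) = 6400 / 115.2 = 55.6 mL/min. He meets the renal entry criterion and is above the 1.5 mg/dL threshold, so the rule is not empty.

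**The case against.** The strongest objection is that the protocol may not contain the error. The point turns on µ versus m in machine-read text, and the digits are exactly what a misread mmol would leave. Small characters are garbled elsewhere: the same sentence has "concentration at the end of infusion for brentuximab vedotin (C_{coi" in Protocol 7.4.18 and "concentration at the end of infusion for brentuximab vedotin (C_{ei" in Protocol 15.6. Other units in 6.2.2 (mmol, nmol, µg) come through sensibly, which makes a misread less likely. That evidence is indirect, though, and only the source page can separate a misread from a typing slip. This part stands and is why the page check comes first.

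The second objection is that little could go wrong. The correct value precedes the faulty one, and 0.133 µmol/L is implausible on its face. The wording is advisory. Entry requires adequate creatinine clearance, creatinine is measured at screening and on Day 1 of each cycle, and the same paragraph of 6.2.2 contraindicates fibrates in kidney failure. If fenofibrate were wrongly reduced, the effect should show in the lipid checks, which cover "fasting cholesterol, and triglycerides at Days 7, 14, 28, 35, and 49 after initiation of bexarotene therapy". All of this stands. It limits the weight of the point but does not make the two figures agree.

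Third, this is a unit-label slip with correct digits rather than a miscalculation. That is fair, and it is why the correction is so small.

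**Conclusion.** The point holds as a minor correction. As rendered, the SI threshold is too small by a factor of about 997 and does not match the 1.5 mg/dL beside it. Either 133 µmol/L or 0.133 mmol/L would be right.

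The size of the error rests on the molar mass of creatinine, and the range tried moves the factor only between 996 and 998. That it is an error in the protocol itself rests on the machine-read unit being faithful to the page, so confidence is moderate. The consequence is confined to the 7-day fenofibrate lead-in for control-arm patients given bexarotene. It has no bearing on the trial's statistical conclusions.

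**What to change.** 1. Check the source page for Protocol 6.2.2. If it reads mmol/L, the matter closes.
2. If it reads µmol/L, restate the threshold as creatinine above 1.5 mg/dL (133 µmol/L). Changing the prefix to give 0.133 mmol/L is equally correct. Send sites a short clarification and carry the wording in the next amendment.
3. If Figure 6-1 repeats the threshold, align it.

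The clinical threshold and the fenofibrate doses stay as they are. The cost is small, with no change to data collection or analysis. Protocol 11.8 requires written ethics approval for protocol changes and does not say whether a unit correction counts as one, so the sponsor should settle that before issuing the clarification. A stand-alone amendment across about 50 centers would be out of proportion.

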6.3 Dose Escalation Rules

No dose escalation of brentuximab vedotin (Arm 1) is permitted in this study. However, in Arm 2 (control arm), the dose of methotrexate or bexarotene may be escalated per treating physician as detailed in the methotrexate or bexarotene product label.

